### **Eating Behavior & Food Craving**

- Eating Disorder Examination-Questionnaire Version (**EDE-Q**). The self-report EDE-Q [61] generates the same overeating data and scale scores as the EDE interview. EDE-Q has good test-retest reliability with BED patients [59, 62, 63]. The EDE-Q converges well with the EDE as a measure of "change" [64].
- Eating Loss of Control Scale (**ELOCS**) [65] assesses the complexity of loss of control eating over the past four weeks. The ELOCS has demonstrated good convergent validity and is considered a valid self-report questionnaire that may provide important clinical information regarding experiences of LOC in people with BED and obesity.
- Three Factor Eating Questionnaire (**TFEQ**) [66] measures eating behaviors with 3 factors: cognitive restraint, disinhibition, and hunger. TFEQ has empirical support [67], and shows differential response across treatments consistent with putative mechanisms [68, 69].

- Yale Food Addiction Scale (YFAS) [70] is a measure of addictive eating behaviors with high fat/sugar foods. Items correspond to the substance dependence diagnostic criteria. The YFAS has demonstrated adequate internal reliability, convergent validity, and incremental validity in predicting binge eating.
- Brief Questionnaire of Food Craving is a measure food craving we developed based on a 10-item Tiffany Questionnaire of Smoking Urges [71] by replacing the word "a cigarette" with "food," and the word "smoke" with "eat."
- Food Craving Inventory (FCI-II) [72] assesses general and specific food cravings and comprises four subscales for different food groups. The FCI has been validated and psychometrically supported in studies with obesity and with obesity/BED groups [72, 73].
- Power of Food Scale (PFS) [74] assesses the psychological impact of and the drive to consume palatable foods in an obesogenic environment. The PFS measures appetite for—rather than the consumption of—palatable foods. The PFS has been validated in large normative (Lowe et al., 2009) and obese samples including weight-loss treatment-seeking obese patients [75]. The PFS comprises 3 scales reflecting food proximity (food available, food present, and food tasted) supported by factor analysis and good test-retest reliability and internal consistency (range 0.81-0.91) [75]. The PFS is a good measure of the hedonic impact of food environment cues; fMRI studies have reported associations with state cravings for desired foods and shifts in brain networks [76].
- Control of Eating Questionnaire is a single item measure to assess perceived control over eating.
- Hunger Ratings is a single item measure 0 to 100 measuring hunger.

### •

### **Health and Behaviors**

- Beck Depression Inventory (**BDI-II**). The BDI [77] is a widely used measure of the symptoms of depression. A voluminous literature has documented good internal consistency (studies range .73 to .95), short-term test-retest reliability, and convergent validity [78].
- Circumplex Scale (**Circumplex**) [79] was modified to a 10-item scale to assess affective state. Participants are asked to provide ratings on how they feel right now for each affect item on a scale ranging from 0 (Not at all) to 100 (Very) on a visual analog scale, and items are classified into positive and negative affective dimensions.
- Medical Outcomes Study Short-Form Health Survey (SF-12) [80] is widely-used measure of health related quality of life. This measure has well-established reliability and validity [81, 82] for physical health and mental health domains.
- Godin Leisure Time Exercise Questionnaire (**Godin**) [83] assesses frequency of mild, moderate, and vigorous physical activity. The Godin has good test-retest reliability [83] and has good support from validation studies using various activity measurements such as activity monitors and maximum oxygen consumption [84].
- Pittsburg Sleep Quality Index (**PSQI**) [85] is a widely used measure of quality and patterns of sleep, assessing namely subjective sleep quality, sleep latency, sleep duration, habitual sleep efficiency, sleep disturbances, use of sleep medication, and daytime dysfunction over the last month. The PSQI has demonstrated good internal consistency and reliability (Cronbach's alpha = .83).
- Alcohol Use Disorders Identification Test (AUDIT-2) [86] is a measure that assesses alcohol use. The AUDIT has been used extensively and demonstrates high internal consistency and good test-retest reliability [87].
- Perceived Stress Scale (PSS) [88] is a measure that assesses how much stress an individual is experiencing. The PSS has a reliable total score ( $\alpha$ =.83), 6-week temporal stability (r=.81) and validity associated with health behaviors including eating [89].

### Safety and Compliance

- Blood Pressure (**BP**) and Heart Rate (**HR**). BP readings (both systolic and diastolic) and HR will be obtained regularly at assessment meetings.
- Systematic Assessment for Treatment Emergent Effects (**SAFTEE**) [90] Adverse events will be assessed in person during study related appointments.
- Columbia Suicide Severity Rating Scale (**C-SSRS**) [91] is a semi-structured assessment intended for administration by clinicians or study staff during scheduled study visits. It explores suicidal ideation and intensity, as well as behaviors and lethality.
- Pill Counts. Participants will be asked to bring their medication to their last appointment and clinicians will count and record the number of pills remaining.
- Naltrexone and Bupropion levels plasma will be collected at weeks 4 and 12 to evaluate plasma trough levels of bupropion, naltrexone, 6-beta-naltrexol levels.

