4. **Research Plan:** Summarize the study design and research procedures using non-technical language that can be readily understood by someone outside the discipline. **Be sure to distinguish between standard of care vs.** research procedures when applicable, and include any flowcharts of visits specifying their individual times and lengths. Describe the setting in which the research will take place.

Overview of Study Design

This single-site, proof-of-concept, clinical trial is a double-blind, placebo-controlled, parallel group study to test the effectiveness of naltrexone + bupropion (NB) pharmacotherapy in BED patients with and without obesity. BED patients with (BMI > 30 and <50) and without obesity (BMI >21.5 and <29.9), will be randomized to NB (32 mg/day naltrexone combined with 360 mg/day bupropion) or placebo (n=50 per cell, n=200 total).

Following eligibility screening and randomization, participants will start a 12-week medication treatment period, a treatment period consistent with other BED medication trials (McElroy et al., 2016). Participants will have four weeks of up-titration: one tablet daily (Naltrexone 8mg/ Bupropion 90mg; 1 week), then two tablets daily (Naltrexone 16mg/ Bupropion 180mg; 1 week), then three tablets daily (Naltrexone 24mg/ Bupropion 270mg; 1 week), to reach the full dose of four tablets daily (Naltrexone 32mg/ Bupropion 360mg). The dosage will continue for the remainder of the 3 months. Medication will be discontinued at the end of 3 months, and patients will then be followed 12-months post-treatment to assess the durability of medication effects. The primary outcome measure is reduction in binge-eating frequency.

To evaluate correlates and mechanisms of NB on eating behavior, assessments will occur in the laboratory and in the field to optimize internal and external validity. Participants will complete human laboratory sessions ("lab sessions") before the start of medication and then during the final week of the 12-week medication period to evaluate the ability to resist eating preferred high-caloric food and subsequent overeating. During the laboratory sessions, we will evaluate potential mechanisms including eating peptides

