### Procedures for Modeling Cue-Induced Eating Behavior.

Each participant will complete two laboratory sessions, the first scheduled prior to starting medication, and the second at the end of medication treatment (week 11-14). This pre-post evaluation by medication group will provide a powerful test of medication effects. Alternatively, if the pre-treatment laboratory session cannot be schedule prior to the beginning of treatment, participants may complete the session around one month of treatment (week 4-6). If we are unable to reschedule at the HRU/CSRU, the lab session will take place at [name] in dedicated lab rooms in [name] research space. Our previous eating study (HIC# 0909005678, [name]) took place in this setting and was very successful. There will be no blood collected throughout the lab session if it occurs at [name], but baseline samples will be obtained on the 4th Floor YCCI unit. All other lab procedures will remain the same. Participants will not be excluded from the treatment study if they are not willing to do the lab sessions, or if they are not able to be scheduled for the lab sessions. Research procedures related to the treatment study (e.g., blood draws for liver function, lipids, and metabolic function) will still be drawn if lab sessions are not completed.

Laboratory sessions will be completed at the Hospital Research Unit (HRU) of the Yale Center for Clinical Investigation (YCCI) located at Yale-New Haven Hospital or the Church Street Research Unit (CSRU) at [name]. Participants will be instructed not to eat past 10:00pm the night before the laboratory session. They will arrive at the HRU/CSRU at 7:30am. At the start of the lab session, participants will have an IV cannula inserted and complete the baseline assessments listed in **Table 1**. Participants will then receive breakfast to standardize time since last food consumption. Breakfast will be a breakfast bar that is approximately 150 calories provided by the Research Team. Participants will then be food deprived for the next 3 hours. Based on our prior work, this length of food deprivation is sufficient to increase food craving. After 3 hours of food deprivation, participants are presented with preferred high-caloric snacks. Participants will be asked to take their study medication prior to the second lab session. Scheduling is limited to HRU/CSRU and participant availability.

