Baseline	7:30am	Urine pregnancy screen, breath alcohol level, CO level, height, weight, vitals,
		mood, food craving, hunger. IV inserted: Estradiol/progesterone (females only),
		liver function, lipids, glucose, insulin, and HbA1c, and overnight fasting levels of
		leptin, ghrelin. Lab 2 Only: Med level, liver function, Lipids, glucose, insulin, and
		HbA1c levels.
	8:00am	Standardized breakfast (no access to food until 11:00am = 3hours of food
		deprivation)
Deprivation	9:00am	Mood, food craving, hunger, vitals
	10:00am	Mood, food craving, hunger, vitals
Food	10:30am	Baseline 1: leptin, ghrelin
Presentation	10:45am	Baseline 2: leptin, ghrelin
	11:00am	Participant presented preferred high-caloric foods. Participant may initiate ad-lib
		eating session or earn money based on de-escalating schedule of reinforcement
		over next 180 minutes
	11:05am	Leptin, ghrelin, mood, food craving, hunger, vitals
	11:15am	Leptin, ghrelin, mood, food craving, hunger, vitals
Ad-lib	11:30am	Leptin, ghrelin, mood, food craving, hunger, vitals will be repeated every 30
Period	12:00pm	minutes during the ad-lib period
	12:30pm	
	1:00pm	**from 11:05am to 2:00pm, whenever the participant decides to 'give in' and
	1:30pm	start eating, we will collect leptin, ghrelin, mood, food craving, hunger, vitals to
	2:00pm	capture the decision point to eat (before eating starts)
Wait Period	2:45pm	Mood, food craving, hunger, vitals
& Discharge	3:20pm	Mood, food craving, hunger, vitals
	3:30pm	Discharge

Procedures for Evaluating Naturalistic Eating Behavior and Stress with Wearable Biosensors.

**Garmin Activity Tracker (Biosensor):** We are collaborating with [name] (UMass) to evaluate ambulatory stress and eating behavior during the first 6-weeks of the treatment phase. We are currently using the same system to monitor stress and alcohol consumption (HIC#2000023970; PI, [name]) and it has been adapted to monitor stress and eating behavior. During the first 6-weeks of the treatment phase, we will assess ambulatory dynamic changes in stress with a wearable biosensor and collect daily information

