# Assessments.

Figure 2. Grid depicting when each assessment is obtained

rigare 2. Oria acpioning	when each assessment is obtained		Р	RE	DURING TREATMENT			Follo	OW-UP			
MEASURE	INSTRUMENT AND REFERENCES	Түре	BASELINE	LAB #1	WEEK 2	MONTH 1	MONTH 2	MONTH 3	LAB #2	6 Момтн	12 Month	BIOSENSOR
Screening Measures							ı		1			
Axis I Disorders	MINI Psychiatric Interview	Interview	*									
Binge-Eating Disorder	EDE Interview	Interview	*					*		*	*	
BMI	Weight, height	RA Eval	*	*	*	*	*	*	*	*	*	
Metabolic Measures	Lipids, HbA1c TSH (as needed)	Blood	*	*					*	*	*	
Safety Measures	Urine screen for pregnancy Urine drug test for opiates	Urine	*									
Menstrual Cycle Data	Menstrual cycle calendar, hormone use, reproductive and gynecological status	Interview	*		*	*	*	*		*	*	
Medical History	Clinical data, incl. start of new treatments	Interview	*					*			*	
Eating Behavior & Food C	Craving											
Eating Disorders	EDE-Q ELOCS	Self-Report	*		*	*	*	*		*	*	*
Eating Behavior	TFEQ YFAS	Self-Report	*			*	*	*		*	*	
Food Craving	Brief Questionnaire of Food Craving FCI-II	Self-Report	*	*		*	*	*	*	*	*	
Drive for Palatable Food	PFS Control of Eating Questionnaire	Self-Report	*	*		*	*	*	*	*	*	
Hunger	Hunger Ratings	Self-Report		*					*			
	Health and Behaviors	0 16 5	*		*	*	*	*	 	*	*	
Depression	Beck Depression Inventory-II	Self-Report	*	*	*	*	*	*	*	*	*	
Affect	Circumplex Scale	Self-Report		Î					Ŷ			+
Quality of Life	Perceived Stress Scale	Self-Report	*			-		*			*	*
Quality of Life	SF-12 Audit-2	Self-Report	*					*			*	
Alcohol Use	Godin Leisure Time Exercise Questionnaire	Self-Report	*					*			*	
Physical Activity Sleep		Self-Report	*	-		-		*			*	
Sieep	Pittsburgh Sleep Quality Index	Self-Report										
Safety & Compliance								 				
Adverse Events	SAFTEE Columbia Suicide Severity Rating Scale	Interview			*	*	*	*				
	Liver Function	Blood		*		*			*			

Page **12** of **49** 

Medication Compliance	Pill Counts	RA Count						*				
	Naltrexone and Bupropion levels	Plasma				*		*				
Vitals	Blood pressure and heart rate		*	*	*	*	*	*	*	*	*	
Placebo Rating	Placebo rating by clinician and participant	Self-Report				*		*				
Assays												
	Leptin, ghrelin, estrogen, progesterone	Blood		*					*			

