### Medication Titration & Taper.

Participants will have four weeks of up-titration: one tablet daily (Naltrexone 8mg/ Bupropion 90mg; 1 week), then two tablets daily (Naltrexone 16mg/ Bupropion 180mg; 1 week), then three tablets daily (Naltrexone 24mg/ Bupropion 270mg; 1 week), to reach the full dose of four tablets daily (Naltrexone 32mg/ Bupropion 360mg).

If participants drop out of the study during, we will ask that they return any unused medication. Participants who have been on the study medication for more than 4 weeks, including those who complete the treatment, will be asked to taper off the study medication: two tablets daily (Naltrexone 16mg/ Bupropion 180mg; 4 days), then one tablet daily (Naltrexone 8mg/ Bupropion 90mg; 3 days), to discontinue medications. Participants on placebo will take the same number of tablets as the active group to maintain the blind. Participants will be cautioned against stopping the medication abruptly. Taper off is not medically necessary for participants on the study medication for 4 weeks or less.

- 12. **Data and Safety Monitoring Plan:** Include an appropriate Data and Safety Monitoring Plan (DSMP) based on the investigator's risk assessment stated below. (Note: the HIC will make the final determination of the risk to subjects.)
  - a. What is the investigator's assessment of the overall risk level for subjects participating in this study? Greater than minimal.
  - b. If children are involved, what is the investigator's assessment of the overall risk level for the children participating in this study? n/a
  - c. Include an appropriate Data and Safety Monitoring Plan. Examples of DSMPs are available here http://your.yale.edu/policies-procedures/forms/420-fr-01-data-and-safety-monitoring-plans-templates for
    - i. Minimal risk
    - ii. Greater than minimal

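### The end-of-treatment drug level is called a week-12 trough, but Table 1 draws it at Lab 2, whose weeks 11-14 window runs into or past the taper; a Lab 2 that late also measures the Aim 2 outcomes on reduced or no drug

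*Combined protocol and SAP*

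**What the plan says.** **Drug level.** Under Measures, Safety and Compliance, the protocol says that "plasma will be collected at weeks 4 and 12 to evaluate plasma trough levels of bupropion, naltrexone, 6-beta-naltrexol levels". The paragraph on monitoring medication compliance gives the same weeks and also calls the levels troughs. In Figure 2 the row "Naltrexone and Bupropion levels" is ticked at Month 1 and Month 3, and the separate Lab #2 column is blank. Table 1, however, has "Lab 2 Only: Med level" in its 7:30am baseline row.

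**Lab 2.** The laboratory procedures section states: "Participants will be asked to take their study medication prior to the second lab session". It gives no hour. It also states: "Participants will not be excluded from the treatment study if they are not willing to do the lab sessions".

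**Window.** The Overview of Study Design places the sessions "before the start of medication and then during the final week of the 12-week medication period". The laboratory procedures section puts the first before medication starts "and the second at the end of medication treatment (week 11-14".

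**Stopping.** The overview stops medication at the end of 3 months. The treatment protocol gives a 7-day taper to anyone treated for more than 4 weeks. Section 11 sets it out as "two tablets daily (Naltrexone 16mg/ Bupropion 180mg; 4 days), then one tablet daily (Naltrexone 8mg/ Bupropion 90mg; 3 days", then nothing.

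**Use.** The supplementary analysis in Section 13 lists plasma levels among its compliance measures. In the active arm it uses their area under the curve to predict binge eating and change in the mechanism variables. Primary Aim 2 analyses latency to eat, calories consumed, leptin, ghrelin and craving from the laboratory sessions.

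**The concern.** Staff following the plan cannot tell which visit supplies the end-of-treatment sample or what dosing state it should represent. Under Figure 2 it is a Month 3 sample, consistent with week 12. Under Table 1 it is a Lab 2 sample, which participants who skip that session do not have, and which may follow a dose or fall in the taper.

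Two analyses are exposed:

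- **Supplementary exposure analysis.** A shift shared by everyone would leave an association unchanged. Variation between people in dose-to-draw time, or in whether the draw precedes the taper, is measurement error in the exposure and would tend to weaken the relation. It cannot be repaired afterwards without dose times.
- **Aim 2.** If Lab 2 is held during or after the taper, the end-of-treatment laboratory outcomes in the active arm no longer reflect full-dose treatment. Any effect that fades with the drug would be understated, and with it the first step of the mediation analysis.

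**Working it through.** The plan states no figure to reproduce. The check is a day count, a dose count, and a rough sizing under assumed kinetics.

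**1. Lab 2 window against the taper.** Weeks 11-14 run from day 10 × 7 + 1 = 71 to day 14 × 7 = 98, which is 28 days. The plan does not say when the 7-day taper starts, so I tried each reading.

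| Reading | Taper days | Window days during or after taper |
|---|---|---|
| Taper follows 12 weeks (day 84) | 85-91 (week 13) | 85-98: 14 of 28, week 14 off drug |
| Taper is the last week of the 12 | 78-84 (week 12) | 78-98: 21 of 28, weeks 13-14 off drug |
| 3 months read as about 91 days, taper follows | 92-98 (week 14) | 92-98: 7 of 28 |

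No reading clears the window. Under the second, even the overview's final treatment week is the taper itself, so restating the overview's wording would not close the gap.

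**2. Dose during the taper (Section 11).** 16/32 = 180/360 = 0.50 for 4 days; 8/32 = 90/360 = 0.25 for 3 days; then 0. These fractions need no kinetic assumption.

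**3. Size of a non-trough level.** The documents give no kinetics, so every input here is an assumption: one compartment, first-order absorption, linear kinetics, steady state and a 12 h interval (the plan says twice daily). With k = ln 2 / half-life,

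C(t) ∝ e^(−ke·t)/(1 − e^(−12ke)) − e^(−ka·t)/(1 − e^(−12ka)), and ratio = C(t)/C(12).

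Example with absorption half-life 3 h, elimination half-life 5 h and t = 1 h: C(1) = 1.0740 − 0.8466 = 0.2274; C(12) = 0.2338 − 0.0667 = 0.1671; ratio = 1.36.

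The taper was handled by superposition: one tablet every 12 h for 4 days, then one each morning for 3 days. Elimination half-lives of 5, 10 and 20 h and draws 0.5 and 1 h after a dose give these levels relative to the full-dose trough:

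| Draw | Absorption half-life 3 h | Absorption half-life 1-6 h |
|---|---|---|
| Full dose, post-dose | 1.04-1.36 | 1.02-2.46 |
| Taper day 4, post-dose | 0.54-0.68 | 0.52-1.23 |
| Taper day 7, post-dose | 0.22-0.32 | 0.20-0.86 |
| 72 h after last tablet | at most 0.04 | at most about 0.05 |

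**4. Effect on a two-sample area under the curve.** The plan does not define the area. If it is formed from weeks 4 and 12 with equal weight, and the two true troughs are equal, it is multiplied by (1 + ratio)/2. At 3 h absorption this is (1 + 1.035)/2 = 1.02 to (1 + 1.361)/2 = 1.18 for a post-dose draw on full dose, and (1 + 0)/2 = 0.50 to (1 + 0.044)/2 = 0.52 for a draw three days off drug.

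**5. Effect on Aim 2.** If a fraction f of active-arm Lab 2 sessions fall late and keep a fraction k of the drug effect, the expected difference is (1 − f) + f·k of its on-treatment size. Neither f nor k can be taken from the documents, so I give no number.

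**The case against.** The strongest reply is that this is one stray table cell. The compliance text, the measures text and Figure 2 all agree on weeks 4 and 12. If the tube is in practice drawn at Month 3, the Lab 2 dosing instruction never touches it. That is fair, and it is why the drug-level part is minor. Table 1 is still the working schedule for the laboratory session and needs correcting.

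Second, the overview's wording and the request to take medication beforehand both suggest that Lab 2 was meant to be on treatment. The intent is probably so. But the detailed procedures allow weeks 13 and 14, and on the first two readings there are no tablets left to take in week 14.

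Third, four stronger readings are tempting and unsupported:

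- *The level is certainly post-dose.* No hour is given. If the last dose was the previous evening's, a 7:30am draw would be close to trough.
- *The post-dose shift is known.* Widening one assumed input takes the full-dose ratio from 1.04-1.36 to 1.02-2.46. At fast absorption and fast elimination, a post-dose level on taper day 4 can exceed the full-dose trough. The model also treats 6-beta-naltrexol like the two drugs, with nothing in the documents to justify that.
- *Participants who taper as told will be classed as non-compliant.* The plan sets no plasma threshold. Discontinuation for non-compliance rests on more than 7 consecutive days of it, and the covariate models use pill counts and time in treatment.
- *Only the supplementary analysis is touched.* The same window governs the Aim 2 laboratory outcomes.

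Finally, a case-report form not provided here may already record dose time.

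**Conclusion.** The inconsistency is real. Followed as written, Table 1 and the laboratory procedures can yield an end-of-treatment level that is not a trough, and can place Lab 2 on reduced or no drug. What is firm is the day count (7, 14 or 21 of 28 permitted days, depending on the taper start) and the dose fractions (50%, 25%, 0%). The concentration ratios are illustrative only. A reader might infer that laboratory sessions were in fact held off drug; the documents show only that this is permitted, and give no count.

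The drug-level conflict is minor, since it bears on a supplementary active-arm analysis with pill counts as a separate check. The Lab 2 window ranks somewhat higher because it touches Aim 2. The primary intent-to-treat comparison of binge eating uses neither the plasma level nor the laboratory session and is unaffected. Confidence is moderate, because which schedule operates in practice cannot be seen.

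**What to change.** 1. **Close the Lab 2 window before the taper.** Require the session on full dose. If it is delayed, extend full dosing until it is done; otherwise flag the session in the Aim 2 analysis. State the same window in the overview and the laboratory procedures, and say when the taper starts. Keep the request to take medication before Lab 2, so that Aim 2 conditions stay as planned.
2. **Name one visit for the end-of-treatment level.** Preferably use the Month 3 / week-12 visit in Figure 2, drawn before that morning's dose and before the taper, and remove the item from Table 1. Alternatively keep it at Lab 2 and stop calling it a trough.
3. **Record time of last dose and time of draw at weeks 4 and 12.** Use time since last dose as a covariate in the supplementary plasma-level models. Exclude or flag samples taken during or after the taper.

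**Cost.** Two data fields, a held morning dose, and possibly one extra venepuncture if the tube is now taken only at Lab 2. Extending full dosing for a delayed session needs extra tablets. The plan allows blood draws at an outside laboratory, so dose-time capture would have to reach any such site used for the week-4 draw. Some samples will drop out of an exploratory analysis. No new assay is needed.
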